1.3 Gameplay Frequency

The study is comprised of two phases.

For **Phase I**, each subject's participation in BioStream Training or play of the alternate game will last for up to 6.67 to 33.33 hours over a 28 day period comprised of up to 20 game play sessions, up to 5 days per week for between 20 minutes and 100 minutes per game play session. The subject will be permitted to complete each daily session through use of the BioStream Training or use of the alternate game at different times throughout each day at the subject's discretion.

For **Phase II**, each subject's participation in BioStream Training or play of the alternate game will last for up to 6.67 to 33.33 hours over a 28 day period comprised of up to 20 game play sessions, up to 5 days per week for between 20 minutes and 100 minutes per game play session. The subject will be permitted to complete each daily session through use of the BioStream Training or use of the alternate game at different times throughout each day at the subject's discretion.

1.4 Relevant Literature and Data

BioStream Training builds on prior literature and shows promise because (1) it incorporates computer games, a medium shown to be particularly promising for helping children with ASD; (2) it leverages educational and behavioral concepts shown to be effective in training social skills; and (3) the social skills currently targeted by BioStream Training, eye contact and emotion recognition, have been shown to be trainable in ways that lend themselves to eye tracking technology.

(1) Video game format

Computers have been shown to be promising teaching tools for children with ASD, and virtual social interactions are thought to have significant potential for improving their real-world social skills [8]. Survey data of subjects that have participated in the BioStream Training has yielded encouraging data with respect to engagement.

(2) Educational and behavioral concepts

BioStream Training leverages the fact that many of the principles shown by research to be effective in teaching and shaping behavior, both generally and in the context of specific social skills, can be directly incorporated into computer-based training. Such principles, including discrete trial training, differential reinforcement, and shaping, are central to BioStream Training, and have an established evidence base, maximizing the likelihood that it will prove efficacious [8, 9].

(3) Social skills targeted, and description of BioStream Training exercises

BioStream Training applies these principles to target social skills including (a) eye contact, and (b) emotion recognition. These have been selected because: they are critical social skills in which children with ASD underperform their typically developing peers; they have been shown to be trainable using methods that can be mimicked in computer-based training [8]; and their training can be augmented through the incorporation of gaze control.

(a) *Eye contact* is the act of looking at someone's eyes during a social interaction. It is important for conveying attention and for communicating social and emotional information [10, 11]. Deficits in eye contact are one of the most notable indicators of ASD [12]. Nevertheless, discrete trial-based training of eye contact is effective, with such interventions having demonstrated increases in eye contact [12, 13]. BioStream Training includes exercises uniquely enabled by gaze control technology that are focused on leveraging these established approaches to help children with ASD improve at making eye contact. For example, during some discrete trials, a character begins speaking to the player, and the player must then look at part of the character's face (e.g. whole face, upper part of the face, eyes) within a certain time increment, for a few seconds, in order to receive a reward.

(b) *Emotion recognition* is the ability to identify human emotions, most typically from facial expressions, and is a crucial component of social development [14]. A meta-analysis found that children with autism underperform their typically developing peers on emotion recognition tasks [15]. There is a pressing need to adapt traditional, manual therapeutic approaches targeting emotion recognition skills to more standardized, computerized delivery platforms. Interventions to date have been effective at driving improvements, some even using video game-based training approaches [8, 14, 16]. BioStream Training leverages one of the more advanced psychophysical paradigms to come out of the experimental psychology literature on face processing: the use of gaze-contingent blurring of facial images, often called the "bubble paradigm." [17, 18] For example, during some exercises, the participant interacts with an animated character whose face is fully or partially blurred. The player must use their gaze to unblur key facial features in order to identify the character's emotion. Then, the player must select the matching emotion from a set of real children's faces.

Assessments

Social Responsiveness Scale-Parent (SRS [19]): The SRS is a parent-report questionnaire that asks parents to rate the frequency of reciprocal social behaviors, communication, and repetitive and stereotypic behaviors in their child. The questionnaire yields a single summary score that can be used as an index of the child's severity of social deficits. This will be completed by a parent during each in-person visit or by telephone with a member of the study team.

Childhood Joint Attention Rating Scale (C-JARS [20]): This is a parent-report measure of joint attention related behaviors in verbal children and adolescents with ASD. This will be completed by a parent during each in-person visit or by telephone with a member of the study team.

Dyadic Interaction Task: There is a lack of standardized validated reference standards for assessing communication-based autism symptoms [21, 22]. Because of this, an exceptionally

large array of assessments is used in the literature. In fact, there are only three standardized tools that have been used in more than 2% of recent trials of autism interventions (none of which are used in more than 7% of studies) [21]. Therefore, in order to determine how we would assess communication skills we worked closely with our team of certified Applied Behavioral Analysis (ABA) therapists, who have years of experience working with children with ASD, and consulted the literature. The task we have constructed follows the Contextual Assessment of Social Skill [23] and procedures developed by Reilly et al [24]. It involves a structured play scenario, which is standard in other similar studies [21, 25-28].

This is an interaction between the subject and a member of the study team where the study team member poses questions to the subject while the interaction is video recorded. Questions may include but are not limited to the following:

What is your birthday? How old are you?
 What do you like to do at school? What do you like about ____?
 What is your least favorite thing at school?
 What do you like to do at home?
 Do you like any sports such as...?”
 Do you have any favorite movies? What’s [that movie] about?
 What’s your favorite program on TV? What’s [that show] about?

In addition to answering questions, subjects may be asked to respond to certain prompts in the context of the dyadic interaction task, sometimes repeatedly. For example, a subject may be prompted to request an object from the study team member conducting the interaction, return the object, and then request that object again.

Further, a subject may be asked by the study team member questions about an object presented. An example of this is a task in which an item is presented to the subject, after presentation, the subject is asked if they would like it placed in a group of items later to be provided to the subject to create something (such as a structure, in the case of building blocks, or 3D art, by laying out different types of objects on a platform such as white board). As the task continues different additional questions are posed to the subject such as the following (in the case of building blocks):

- 1) “What’s your favorite color?”
- 2) “What do you like to build with blocks?”
- 3) “What are you going to build with your blocks?”
- 4) “Which shape block do you like the best?”
- 5) “What do you think you’re going to build today with these blocks?”

After completion of the task, the subject is then permitted to complete the activity, which in the above example, is using the building blocks to create something. Each dyadic interaction will last up to 10 minutes.

During the Dyadic Interaction Task the study team member sits directly across from the subject while wearing a pair of video recording glasses (with the lenses in place or removed) that has a video camera embedded in the bridge of the glasses (such as the Pivothead Kudo Glasses or the Pivothead Durango Glasses) [26, 27]. The study team member activates the

video recording function of the glasses prior to starting the task so that the entire task is recorded. Alternatively or in conjunction with the video recording glasses, single or multiple video cameras may be used to record the task.

Following each Dyadic Interaction Task the video recording file is transferred from the glasses to a data storage device and/or computer maintained by the study team member for subsequent analysis. This analysis may include use of video annotating software such as the BORIS or ELAN video annotating software to annotate different conditions within each frame or group of frames of the video recording which conditions may include: the orientation of the subject's face is oriented towards the camera, the orientation of the subject's face is not oriented towards the camera, the orientation of the subject's eyes are oriented directly toward the camera, the orientation of the subject's eyes are not oriented directly toward the camera, and the subject matter of the video is not applicable. Any member of the study team or third parties with HIPPA compliant policies and procedures, blinded to the study group of each subject, may engage in the above-described annotation including therapist practitioners or research organizations.

Eye Tracking Video Assessment: This task involves the subject viewing social scenes and other types of scenes on a computer monitor while eye gaze patterns and fixations on social (i.e. face) and non-social portions of the scene are measured using an eye tracker. This is similar to eye tracking assessments used in ASD diagnosis research in which measurements of the percent of time looking at faces and eyes while watching video clips are obtained. [29]

Ekman 60 Faces Test: (Ekman & Freisen 1976 [30]), using a selection of 60 photographs from Ekman's Pictures of Facial Affect [30]. These images have been used in several studies of emotion recognition [31, 32]. Subjects will be presented with 60 photographs of different individuals expressing different emotions and asked to label each of the photographs in terms of the emotion expressed with one of the six standard emotional labels: happiness, sadness, anger, surprise, disgust, and fear. This assessment may be administered by computer and the study team member administering the assessment may assist in entry of the subject's selection.

Emotional Expression Video Assessment: This task involves the subject viewing videos of scenes where actors exhibit a specific emotion and following each video the subject is asked to label the emotion presented from a group of choices (ie. happiness, sadness, anger, surprise, disgust, and fear) during the assessment eye gaze patterns and fixations are measured using an eye tracker. This is similar to the Ekman 60 Faces Test but adds a level of realism as the emotions expressed are in video form. This is also similar to eye tracking assessments used in ASD diagnosis research in which measurements of the percent of time looking at faces and eyes while watching video clips are obtained [29].

Test of Variables of Attention (TOVA [33]): The TOVA is a highly reliable, computerized neuropsychological measure of sustained attention and response inhibition. This continuous performance measure presents a target and non-target stimulus, and children are instructed to only press the button when they see the target presented. Study members will ask and take

note of the subject's caffeine consumption the day of administration of each TOVA and may note the subject's amount of sleep the night before administration of each TOVA and incidental use of antihistamines or anxiolytic medications, as caffeine consumption, amount of sleep, and use of use of antihistamines or anxiolytic medications, can impact the outcomes of the test.

Peabody Picture Vocabulary Test, 4th Edition (PPVT [34]): The PPVT-4 scale is a norm-referenced, wide-range instrument for measuring the receptive (hearing) vocabulary of children and adults. Enlarged and colorized, this PPVT edition is available in two parallel forms (form A and form B) that are administered individually. Each form contains training items and 228 test items, each consisting of four full-color pictures as response options on a page. For each item, the examiner says a word, and the examinee responds by selecting the picture that best illustrates that word's meaning.

Video Recording of Study Visits: All study team member visits to the home, school, therapy center, or research organization may be video recorded using a single or multiple video cameras and tripods.

Data Collection – Behavioral Data

Eye Tracking: Study participants will be positioned so measurements can be obtained using an eye tracking device available for purchase by consumers e.g. the Tobii Eye Tracker 4C. This device uses a camera to measure eye positions and gaze direction to trace where study participants are focused (point of gaze) as they look at stimuli presented on a screen. The device may also measure pupil dilation.

Behavior: Recorded behavioral measures may include computer mouse click, computer keyboard/touchscreen keystroke, touchscreen contact, and game controller game play data.

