Additionally, subject eye contact video recording data may also be collected using a video camera and/or video camera embedded glasses worn by any member of the study team during real world dyadic interaction task assessment. **This data will not be stored on or collected using the Subject Computer. This data will be stored on a separate computer and/or computer data storage device maintained by any member of the study team. This data may also be sent to HIPAA compliant third parties including therapist practitioners or research organizations. These HIPAA compliant third parties, blinded to the study group of each subject, will be used to annotate the video recordings of the dyadic interaction task assessments including for subject eye contact during the task.**

Certain Parent assessment and survey data may be collected using a computer (**excluding the Subject Computer except in the case of the Weekly Parental/Teacher/Therapist Survey**) and/or manually using handwritten paper-based data collection methods. The parent or teacher or therapist (as applicable) may complete a Weekly Parental/Teacher/Therapist Survey using a form on the Subject Computer. **This survey is configured so that only de-identified data may be included in the survey or associated with the survey.**

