2 STUDY OBJECTIVES

2.1 Primary Objective (or Aim)

The primary objective of this study is to determine whether 6.67 to 33.33 hours of BioStream Training improves the performance of children with ASD on social skills assessments including in comparison to an alternate game. Specifically with respect to the following:

The mean change from baseline score on the following assessments based on post-final game play session assessment compared to the alternate game group:

- a. Subject gaze patterns as measured by video eye tracking assessment.
- b. Subject gaze patterns as measured by the dyadic interaction task.
- c. Mean change in baseline score on the Ekman 60 Faces Test.
- d. Mean change in baseline score on the TOVA.
- e. Mean change in baseline score on the SRS.

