5.5 Primary Endpoint

Paired-sample t-tests will be used to measure changes from baseline within each group, and independent sample t-tests will be used to measure changes from baseline relative to the alternate game group for all endpoints.

For all endpoints, we will determine whether there were statistically significant changes in scores from baseline or relative to the alternate game group. Significance will be set at $p < 0.05$. Multiplicity of primary endpoints will be managed via statistical corrections.

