7.3 Confidentiality

All written or electronic forms (except Informed Consent Forms and Assent Forms) will employ a unique alphanumeric identifier; in no case will the participant's name or other identifying information appear on these forms. The user ID for the BioStream Training and alternate game shall use the same unique alphanumeric identifier. The study team will accomplish this on all parent/guardian or teacher or therapist questionnaires (as applicable) which have lines for child and parent name by applying a label with unique alphanumeric identifier and instructing parents/guardians or teacher or therapist to use generic labels (e.g., biological mother) rather than writing their names. The PI will keep a master list containing PHI and subject ID number separate from coded data forms, which will be maintained in a locked file drawer, cabinet or lock box in the PI's office. Only the PI will have access to this location. The master list will be maintained on a separate password-protected computer and be stored in an encrypted password protected file. Video recordings will stored on password-protected and/or encrypted data storage devices including computers, external hard drives, and/or flash drives only accessible by members of the study team including the Sponsor's study team members. Any member of the study team or third party with HIPPA compliant policies and procedures, blinded to the study group of each subject, may engage in in video recording annotation including therapist practitioners or research organizations. The Sponsor may collect and store all de-identified data on password-protected and/or encrypted data storage devices including computers, external hard drives, and/or flash drives.

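### Masking of dyadic video annotators to visit, and the order of coding, are not specified, which leaves the planned within-group paired tests of a primary endpoint open to coder bias

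*Combined protocol and SAP*

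**What the plan says.** **Masking.** Annotation is described in three places, and each masks to group only.

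- Section 1.1, on outside annotators: "blinded to the study group of each subject, will be used to annotate the video recordings of the dyadic interaction task assessments".
- Section 1.4, Dyadic Interaction Task: coding is open to "Any member of the study team or third parties with HIPPA compliant policies and procedures". The masking condition attached to that pool reads: "blinded to the study group of each subject, may engage in the above-described annotation".
- Section 7.3 names the same pool, "Any member of the study team or third party with HIPPA compliant policies and procedures". It attaches the same masking condition: "blinded to the study group of each subject, may engage in in video recording annotation".

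No section mentions masking to visit, removal of visit or date labels, coding order or double coding. Section 3.2 has blinding in its heading but contains only the sentence on random assignment.

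**What is coded.** Annotators judge frames or groups of frames, for example whether "the orientation of the subject's eyes are oriented directly toward the camera". After each task the recording is moved to storage kept by the study team member, for later analysis.

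**Where the score is used.** Section 2.1 lists "Subject gaze patterns as measured by the dyadic interaction task" as primary endpoint b, defined as mean change from baseline compared with the alternate game group. Section 5.5 adds: "Paired-sample t-tests will be used to measure changes from baseline within each group", with independent-sample t-tests for the comparison between groups. Sections 5.5 and 5.7.2 look for significance either from baseline or against the alternate game group. The SAP supplement adds mixed ANOVAs for the Ekman 60, SRS and C-JARS but not for dyadic gaze, so this endpoint rests on the t-tests.

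**The concern.** Masking to group protects the contrast between groups. It does nothing for a contrast between before and after, because the information that could sway the coder there is which visit the video comes from. In Phase I the task is recorded at Visits 2 to 6, with Visit 2 as baseline. The protocol leaves open whether a coder can see the visit and whether a child's videos are scored in visit order.

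If coders expect more eye contact later, or if their threshold for direct gaze loosens as coding proceeds in visit order, later videos score higher with no change in the child. That shift goes directly into the mean change that the paired test examines. Because the plan treats a significant change from baseline as a finding in its own right, an artefact of coding could be reported as a positive result on a primary endpoint.

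**Working it through.** The plan gives no power calculation, effect size or SD of change for this endpoint, so there is no stated figure to reproduce. The calculation below is an illustration.

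**Inputs from the documents**
- Up to 150 participants (Section 5.8) in two groups (Section 3.2).
- Significance level 0.05, with an unnamed correction across primary endpoints (Section 5.5).
- Five primary endpoints (Section 2.1).

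**Assumptions**
- 1:1 allocation and no loss, so n = 150 / 2 = 75 analysed per arm.
- Two-sided tests.
- No true change in the child.
- Videos after baseline are coded higher by b, in units of the SD of change. The documents give no value, so b is varied.
- Where a corrected level is shown, Bonferroni: 0.05 / 5 = 0.01.

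**Paired test in one arm.** The statistic follows a non-central t with n − 1 = 74 degrees of freedom and non-centrality b√n = b × 8.660. Rejection probability = P(|T| > t*), with t* = 1.993 at 0.05 and 2.644 at 0.01.

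| b (SD of change) | b√75 | Rejection at 0.05 | Rejection at 0.01 |
|---|---|---|---|
| 0 | 0 | 5% (2.5% as improvement) | 1% (0.5% as improvement) |
| 0.1 | 0.866 | 13.7% | 4.2% |
| 0.2 | 1.732 | 40.1% | 18.9% |
| 0.3 | 2.598 | 72.7% | 48.6% |

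For b above zero, nearly all rejections are in the direction of improvement; at b = 0.1 and level 0.05 the share is 13.5 of the 13.7 points. The smallest observed shift that reaches p < 0.05 is 1.993 / 8.660 = 0.23 SD.

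**Fewer children analysed.** Section 5.7.2 needs both initial and final visit data. With 50 per arm at 0.05, rejection is about 28% at b = 0.2 and 55% at b = 0.3.

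**Between-arm test.** Write the true mean changes as δ₁ and δ₂. With the same shift in both arms, the difference in mean change is (δ₁ + b) − (δ₂ + b) = δ₁ − δ₂, so b drops out. A simulation of 20,000 trials with 75 per arm and no true change agrees: the independent t-test rejects in 4.8%, 5.0%, 4.9% and 4.9% of trials at b = 0, 0.2, 0.3 and 0.5.

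**The case against.** **Silence is not unmasking.** A reader might infer that coders know which video is the later one. The documents do not say so. They state no coding order, timing or labels, and moving a file to storage after each task says nothing about when it is scored. This stands: the defect is a missing specification.

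**Study team members as coders.** A reader might also infer that staff who know the child's arm may code, and that bias can therefore enter the comparison between arms. The text does not support this. In Sections 1.4 and 7.3 the condition of being blinded to study group most naturally covers study team members as well as third parties, so someone who knows the arm does not qualify. What remains is practical. Study team staff review the child's training or alternate game with the supervising adult at Visit 1 (Section 3.1.2) and may ask the child about the assigned game at visits (Section 5.4.1). No procedure says how such people are kept from coding.

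**The endpoint's own contrast is protected.** Section 2.1 defines the endpoint against the alternate game group, and a common shift cancels there. This stands and confines the harm to the paired tests.

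**The illustration depends on its assumptions.** Smaller numbers or a corrected significance level lower the rates, as shown. Correction for multiplicity does not remove the bias, though: at 0.01 and b = 0.3 rejection is still 49%.

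**Visit masking does not rescue a before-after test.** Practice on a repeated task, familiarity with the examiner and the passage of time would remain whoever codes. This also stands, and is why the fix must deal with the role of the paired tests as well.

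**Conclusion.** The point holds as a gap in specification. Annotators are required to be masked to group, while visit and coding order are left open, for a human-coded primary endpoint on which a within-group change counts as a result. Under the stated assumptions (75 analysed per arm, 1:1 allocation, no loss, two-sided), coder shifts of 0.1 to 0.3 SD of change raise paired-test rejection from 5% to about 14% to 73%. At an assumed Bonferroni level of 0.01, the rise is from 1% to about 4% to 49%. The size of any coder shift is unknown.

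It would be wrong to conclude that the randomised comparison is damaged. If the stated group masking is kept, a shift tied to visit is the same in both arms and that comparison stays at about 5%. The change is worth making because it is cheap and removes one source of bias from a planned test of a primary endpoint.

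**What to change.** 1. In Sections 1.4 and 7.3, mask annotators to visit as well as group. Give each video a random file code carrying no visit number or date, and code each child's videos in random order after that child's last visit.
2. In the same sections, to make the stated group masking workable, do not let anyone who introduced the game to a child, or ran that child's visits, code that child's videos.
3. In Sections 5.5 and 5.7.2, base the efficacy conclusion on the between-group test and label the paired tests descriptive.

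The cost is file renaming, a shuffled work list and later coding. Third-party annotators are already provided for, but the documents give no staffing, so whether item 2 needs more people cannot be judged from them. Item 3 costs nothing in data collection; it gives up the option of claiming efficacy from a change within one arm.
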